#### 8.3.1.2 Main Estimation

The GA lesion area (at baseline, Week 24, and Week 52) will be analyzed using a random coefficients model. The model includes terms for time (continuous variable assuming linearity) and treatment-by-time interaction. The intercept and slope of time are assumed to

be random effects with a bivariate normal distribution and an unstructured (UN) covariance matrix while the treatment-by-time interaction is assumed to be a fixed effect. CCI

Within the framework

of this model, a point estimate of the treatment group difference in the regression slope between each NGM621 group and the pooled Sham group will be provided.

[figure not shown]
The corresponding two-sided 95% confidence interval and p-value for the point estimate will also be presented.

A hierarchical testing procedure will be used to control the family-wise type-I error rate associated with the tests of the two NGM621 groups (NGM621 Q4W vs pooled Sham and NGM621 Q8W vs pooled Sham). Specifically, the comparison between NGM621 Q4W and pooled Sham will be performed first. If this test is statistically significant at the 5% level, then the comparison between NGM621 Q8W and pooled Sham will be performed. If the first test is not statistically significant at the 5% level, then the comparison between NGM621 Q8W and pooled Sham will be considered exploratory.

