#### **5.2.1.2 Fellow (Non-study) Eye**

11. Any history of or active choroidal neovascularization (CNV) less than 2 years in duration. CNV of greater than 2 years since clinical diagnosis is permitted for up to 25% of the total patient population. Permitted CNV can be receiving active treatment (e.g., anti-VEGF).

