## **6.3            Randomization**

After written informed consent has been obtained, all subjects will receive a subject identification assigned through the Interactive Response Technology (IRT).

A subject must satisfy all eligibility criteria prior to randomization. As part of the screening process, the central reading center (masked to subject treatment assignment) will evaluate FAF, CFP, SD-OCT, and FA images to provide an objective, masked assessment of subject eligibility. In addition, treatment assignment/regimen will be masked to the specific site personnel, study subjects, sponsor study team, and sponsor Medical Monitor throughout the study period. After all subject eligibility requirements are confirmed, site personnel will contact the IRT on Day 1 visit for assignment of the study treatment (NGM621 or Sham). Subjects will be randomized in a 2:1:2:1 ratio to one of the study treatments arms (NGM621 Q4W, Sham Q4W, NGM621 Q8W, or Sham Q8W). The randomization will be stratified by subjects' baseline CNV status (Yes/No) in the fellow (non-study) eye. The subjects will be randomized on the same day the study treatment is to be initiated (Day 1 visit).

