### 7.3.7 BCVA/LLVA

Best corrected visual acuity will be measured by trained and certified personnel at the study sites. The visual acuity (VA) examiner must be masked to each subject's study (treated) eye and treatment arm (study drug vs. Sham) assignment. VA will be measured at the intervals specified in [Table 4](#) and [Table 5](#).

The name and certification number of the vision examiner should be documented in the subject's visual acuity (VA) worksheet (provided by the Sponsor or designee) at each visit. Retroilluminated ETDRS charts are used in this trial. Refraction should be conducted prior to visual acuity testing to obtain best-corrected vision. Best-corrected visual acuity at a starting distance of 4 meters is measured at all office-based study visits using standard charts, lighting, and procedures. The low luminance visual acuity (LLVA) has the same requirements as the best corrected visual acuity; however, the low luminance visual acuity will be measured by placing a 2.0-log-unit neutral density filter over the best correction for that eye and having the participant read the normally illuminated Early Treatment Diabetic Retinopathy Study chart.

A description of the VA assessment is detailed in the Study Procedure Manual or equivalent.

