## 8 Statistical Considerations

A detailed statistical analysis plan (SAP) will be provided and finalized prior to the study database lock or unmasking. No discrepancies are expected between the SAP and the protocol. However, if there are discrepancies between this section of the protocol and the final SAP, the SAP will override the protocol.

In general, descriptive statistics including the number of non-missing observations (n), arithmetic mean (mean), standard deviation (SD), median, minimum (min), and maximum (max) will be presented by treatment group for continuous endpoints. Frequency and percentage distribution will be presented by treatment group for categorical endpoints.

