### **8.3.2 Secondary Efficacy Analyses**

Secondary efficacy endpoints include change from baseline at Week 52 in GA lesion area, the square root of GA lesion area, BCVA score, LLVA letter score, LLD in EDTRS letters at a starting distance of 4 meters, binocular reading speed (by MNRead or Radner reading charts), binocular critical print size (by MNRead or Radner reading charts), FRI composite score, and NEI VFQ-25, as well as change and percent change of CH50 from baseline at each visit.

The change from baseline will be analyzed using a linear mixed-effects model. The model includes fixed effects for treatment, visit, treatment-by-visit interaction, and the baseline outcome value as a covariate. The covariance structure for this model will be assumed to be unstructured. If the model does not converge under this assumption, then a compound symmetry covariance structure will be used. Within the framework of this model, a point estimate of the treatment group difference at Week 52 between each NGM621 group and the pooled Sham group will be provided. The corresponding two-sided 95% confidence interval and p-value for the point estimate will also be presented.

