#### **8.6 Sample Size Determination**

Subjects will be randomized in a 2:1:2:1 ratio to receive treatment with NGM621 Q4W, Sham Q4W, NGM621 Q8W, or Sham Q8W. Subjects from the two Sham groups will be pooled in the data analysis.

A sample size of 106 subjects per treatment group (i.e., 318 subjects in total) is expected to provide approximately 90% (NGM621 Q4W vs pooled Sham) and 85% (NGM621 Q8W vs pooled Sham) power to detect a statistically significant treatment group difference in the rate of change in GA lesion area over the 52 weeks of treatment. The power is estimated based on simulations assuming a mean GA lesion area of 8 mm^2 at baseline for all subjects, a common standard deviation of 4 mm^2 for GA lesion area, a linear slope of 2 mm^2 per year for the

pooled Sham group, 1.4 mm^2 per year for NGM 621 Q4W and 1.45 mm^2 per year for NGM 621 Q8W, a within-subject correlation of 0.95, a statistical significance level of 5% (two-sided), and a 10% of subject dropout rate. These assumptions are based on published data

CCI

CCI

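### Randomization is stratified by fellow-eye CNV, but neither the primary nor the secondary efficacy model includes it; if CNV predicts GA growth, the reported SE is slightly too large

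*Combined protocol and SAP*

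**What the plan says.** Section 6.3 (Randomization) names one stratification factor: "The randomization will be stratified by subjects' baseline CNV status (Yes/No) in the fellow (non-study) eye". Section 5.2.1.2 (Fellow Eye) limits how common the positive stratum can be: "CNV of greater than 2 years since clinical diagnosis is permitted for up to 25% of the total patient population".

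The primary analysis in Section 8.3.1.2 is a random coefficients model for GA lesion area at baseline, Week 24 and Week 52: "The model includes terms for time (continuous variable assuming linearity) and treatment-by-time interaction". Intercept and slope are random. Part of that section is blacked out, but the Synopsis prints the same stretch in full. It deals with the covariance fallback and the error assumptions and adds no stratum term.

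For the secondary endpoints, Section 8.3.2 states: "The model includes fixed effects for treatment, visit, treatment-by-visit interaction, and the baseline outcome value as a covariate". No CNV term appears there or in the corresponding Synopsis text.

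Section 8 adds that "if there are discrepancies between this section of the protocol and the final SAP, the SAP will override the protocol". No separate SAP text was available, so this point concerns the models as the protocol states them.

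**The concern.** When randomization is stratified by a prognostic factor, the arms are balanced on it, and the true sampling spread of the treatment contrast excludes the variation between strata. A model without the factor still counts that variation as residual, here as random-slope variance. Its standard error is then larger than the real spread, its confidence interval too wide, and its test rejects less often than the nominal 5%.

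The primary contrast is a difference in slopes, so only a CNV-by-time term removes the excess. A CNV main effect alone shifts the intercept.

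Precision and power are at stake, not validity. The Q8W comparison is formally tested only if Q4W succeeds, so precision lost on Q4W also affects Q8W.

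**Working it through.** **Inputs from Section 8.6.** SD of lesion area 4 mm²; 106 subjects per analysis group after pooling Sham; slopes of 2, 1.4 and 1.45 mm²/yr, so the effects are 0.60 (Q4W) and 0.55 (Q8W); and "a within-subject correlation of 0.95, a statistical significance level of 5% (two-sided), and a 10% of subject dropout rate".

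**Assumed inputs.** The slope difference between CNV strata, g, is not in the documents; the range shown is 0 to 1.0 mm²/yr. The CNV-positive share p is taken as 25% (the cap, hence the largest case) and 10%.

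**Reproducing the stated power**
- Variance of one-year change: V = 2 × 4² × (1 − 0.95) = 1.60, SD 1.265.
- Subjects per arm after dropout: n = 106 × 0.9 = 95.4.
- SE of the difference: SE_u = √(2 × 1.60 / 95.4) = 0.183; 95% CI half-width 1.96 × 0.183 = 0.359.
- Power = Φ(effect/SE_u − 1.96): 90.6% for Q4W and 85.2% for Q8W taken alone. The plan states about 90% and 85%, so its figures are reproduced.

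**Effect of omitting the stratum.** V is held at 1.60 and exact balance within strata is assumed.
- Removable variance: r = g² p(1 − p). Example: g = 0.5, p = 0.25 gives 0.0469, which is 2.9% of V.
- Adjusted SE: SE_a = √(2(V − r)/n). Example: √(2 × 1.5531 / 95.4) = 0.180.
- SE excess = SE_u/SE_a − 1.
- Type I error of the unadjusted test = 2(1 − Φ(1.96 × SE_u/SE_a)).
- Power, unadjusted = Φ((effect − 1.96 × SE_u)/SE_a); adjusted = Φ(effect/SE_a − 1.96).

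At p = 25%:

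| g (mm²/yr) | SE too large by | Half-width if adjusted | Type I error, unadjusted | Q4W power, unadj → adj | Q8W power, unadj → adj |
|---|---|---|---|---|---|
| 0 | 0 | 0.359 | 5.0% | 90.6% (no change) | 85.2% (no change) |
| 0.25 | 0.4% | 0.358 | 4.9% | 90.7 → 90.8% | 85.2 → 85.4% |
| 0.5 | 1.5% | 0.354 | 4.7% | 90.9 → 91.4% | 85.5 → 86.2% |
| 0.75 | 3.5% | 0.347 | 4.3% | 91.3 → 92.4% | 86.0 → 87.4% |
| 1.0 | 6.4% | 0.337 | 3.7% | 91.9 → 93.7% | 86.7 → 89.2% |

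From unrounded values, the gain from adjustment for g = 0.25, 0.5, 0.75 and 1.0 is 0.1, 0.5, 1.0 and 1.7 points (Q4W) and 0.2, 0.7, 1.5 and 2.5 points (Q8W). At p = 10%, the SE is too large by 0.2%, 0.7% and 2.9% for g = 0.25, 0.5 and 1.0.

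**Simulation of the stated model** (8,000 trials per scenario, 95 per arm, visits at Weeks 0, 24 and 52, strata exactly balanced, no treatment effect, p = 25%)
- g = 1.0, stated model: mean reported SE 0.181 against an empirical SE of 0.171; rejection 3.7%.
- g = 1.0, CNV main effect only: rejection 3.8%, so the conservatism stays.
- g = 1.0, CNV and CNV-by-time: rejection 5.1%.
- g = 1.0, unstratified randomization and no adjustment: rejection 5.3%. The conservatism therefore comes from stratifying without adjusting.
- g = 0.5: rejection 5.4% unadjusted and 5.6% with both terms. The predicted effect is too small to separate from simulation noise, so that row rests on the formula.

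**Secondary GA-area change at Week 52.** With baseline as covariate, V = 16 × (1 − 0.95²) = 1.56. For g from 0.25 to 1.0, the SE is too large by 0.4% to 6.6% at p = 25% and by 0.2% to 3.0% at p = 10%. This assumes that CNV status is independent of baseline area and that the comparison model includes CNV-by-visit. The other secondary endpoints cannot be quantified because the documents give no SDs for them.

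**The case against.** The strongest reply is that the premise is not in the documents. Nothing says fellow-eye CNV predicts study-eye growth, and no reason is given for choosing it as the stratification factor. The larger figures need g = 1.0, which is half the assumed Sham slope and above both assumed drug effects, together with the CNV share at its cap. For g up to 0.5 the gain is under one point of power, and simulation cannot show the type I error effect there. The stated power is reached without adjustment. Exact balance among completers is also assumed; dropout and replacement of discontinued subjects could disturb it and make the conservatism smaller. Finally, the SAP may already contain the term.

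Most of this stands as a limit on size: the effect is conditional and probably small, and the figures for g of 0.75 and 1.0 are upper bounds. It does not remove the mismatch between how subjects are randomized and how they are analysed, and it gives no reason to keep the factor out. If CNV status carries no information, adjusting for it costs almost nothing.

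A narrower objection is that the secondary GA-area figures assume CNV-by-visit while a main effect is the minimum proposed. The difference is negligible: a main effect alone removes about 93% of the stratum variance at Week 52.

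**Conclusion.** The point holds. The only stratification factor is missing from both stated efficacy models. If it predicts GA growth, the primary SE is overstated and the test mildly conservative: by 1.5% and to about 4.7% at g = 0.5 with 25% CNV-positive, and by 6.4% and to 3.7% at the upper bound g = 1.0. If it does not, there is no loss. These sizes depend on an assumed g and on balanced strata. The treatment estimate is not biased, type I error is not inflated, and the sample size remains adequate. This is a change that should be made because it aligns the analysis with the design at almost no cost; it does not threaten validity. Confidence is high on the omission and its direction. Its size cannot be settled from the documents.

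**What to change.** In the primary random coefficients model, pre-specify fellow-eye CNV status and CNV-status-by-time as fixed effects. Both are needed, because the main effect alone does not correct the slope SE. In the secondary mixed model, add CNV status as a main effect. CNV-by-visit is optional: it suits GA area, where a growth difference widens between Weeks 24 and 52. Carry the same terms into the imputation-based sensitivity analyses. State all of this in the SAP before unmasking, or confirm that the SAP already does so.

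The cost is two parameters in the primary model and one in the secondary. With CNV-by-visit, the secondary total is two for endpoints measured only at Weeks 24 and 52, but about 14 for BCVA, because "Best-corrected visual acuity at a starting distance of 4 meters is measured at all office-based study visits" (14 post-baseline visits through Week 52 in the Q4W arms, 9 in the Q8W arms). No new data are needed, since CNV status is already recorded for randomization. The change is a few lines of text.

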### ***Main Estimation***

The GA lesion area (at baseline, Week 24, and Week 52) will be analyzed using a random coefficients model. The model includes terms for time (continuous variable assuming linearity) and treatment-by-time interaction. The intercept and slope of time are assumed to be random effects with a bivariate normal distribution and an unstructured (UN) covariance matrix while the treatment-by-time interaction is assumed to be a fixed effect. If there is a convergence issue under the assumed covariance structure (UN) for the random effect, then a variance-components covariance structure will be used. The within-subject errors are assumed to be independent and identically distributed normal random variables and are assumed to be independent of the random intercept and random slope. Within the framework of this model, a point estimate of the treatment group difference in the regression slope between each NGM621 group and the pooled Sham group will be provided. The corresponding two-sided 95% confidence interval and p-value for the point estimate will also be presented.

A hierarchical testing procedure will be used to control the family-wise type-I error rate associated with the tests of the two NGM621 groups (NGM621 Q4W vs pooled Sham and NGM621 Q8W vs pooled Sham). Specifically, the comparison between NGM621 Q4W and pooled Sham will be performed first. If this test is statistically significant at the 5% level, then the comparison between NGM621 Q8W and pooled Sham will be performed. If the first test is not statistically significant at the 5% level, then the comparison between NGM621 Q8W and pooled Sham will be considered exploratory.

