## 5 Subject Selection

### 5.1 Inclusion Criteria

Subjects who meet the following criteria will be included in the study:

1. Male or female (non-pregnant, non-lactating) subjects  $\geq 55$  of age
2. Standard luminance BCVA score of 34 letters or better using ETDRS charts at the starting distance of 4 meters (approximately 20/200 Snellen equivalent or better) in study eye
3. Clinical diagnosis of GA secondary to AMD with the GA lesion meeting the following criteria as determined by the central reading center's assessment of Fundus Autofluorescence (FAF) imaging at screening:
  - a) Total GA area must be  $\geq 2.5$  and  $\leq 17.5 \text{ mm}^2$
  - b) If GA is multifocal, at least one focal lesion must be  $\geq 1.25 \text{ mm}^2$  (0.5 DA), with the overall area of GA  $\geq 2.5$  and  $\leq 17.5 \text{ mm}^2$
  - c) The entire GA lesion must be completely visualized on the macula-centered image and must be able to be imaged in its entirety and not contiguous with any areas of peripapillary atrophy.
  - d) Presence of banded or diffuse pattern of hyper-autofluorescence in the junctional zone of GA. Absence of hyper-autofluorescence in the junctional zone of the GA (i.e., pattern = none) is excluded.
  - e) Well demarcated GA with no anatomical evidence (as assessed by FA and SD-OCT) of current or prior CNV in the study eye
4. Clear ocular media and adequate pupil dilatation and fixation in both eyes to permit good quality photographic imaging
5. Female subjects must be either of a) non-childbearing potential, defined as women who have had a hysterectomy, bilateral oophorectomy, medically documented ovarian failure, documented postmenopausal, or a follicle stimulating hormone  $> 40 \text{ mIU/mL}$ , or b) if of childbearing potential, defined as women with  $< 2$  years of amenorrhea (absence of menstruation), then must have a negative serum pregnancy test at Screening and urine pregnancy test at the Day 1 visit prior to first dose of study drug.
6. Female subjects of childbearing potential and male subjects with a female partner of childbearing potential must either be abstinent or be using consistent and adequate birth control from Screening to End of Study (EOS / Week 56). One of the following forms of contraception is required:

- a) Condom
- b) Hormone-containing contraceptive
- c) Intrauterine device with a failure rate < 1% per year
- d) Cervical cap or diaphragm with spermicidal agent
- e) Tubal sterilization
- f) Vasectomy in male partner

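### The primary slope model uses no baseline lesion feature other than area, although focality and junctional-zone pattern fall within the reading centre's screening assessment; adding them by time is a cheap gain of unknown size

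*Combined protocol and SAP*

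**What the plan says.** **Primary model.** Section 8.3.1.2 states that "The GA lesion area (at baseline, Week 24, and Week 52) will be analyzed using a random coefficients model". On the fixed terms it states that "The model includes terms for time (continuous variable assuming linearity) and treatment-by-time interaction". Intercept and slope are random with an unstructured covariance. Part of the paragraph in 8.3.1.2 is redacted, but the synopsis prints it in full. What it adds there is a fallback, "If there is a convergence issue under the assumed covariance structure (UN) for the random effect, then a variance-components covariance structure will be used", and assumptions about the within-subject errors. The redaction therefore hides no covariate.

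**Screening assessment.** Section 5.1, criterion 3, sets the lesion criteria "as determined by the central reading center's assessment of Fundus Autofluorescence (FAF) imaging at screening". Two of them concern lesion features other than total area:
- 3(b): "If GA is multifocal, at least one focal lesion must be" at least 1.25 mm².
- 3(d): "Presence of banded or diffuse pattern of hyper-autofluorescence in the junctional zone of GA". Eyes with no such pattern are excluded.

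**Randomization.** Section 6.3 has a single stratum: "The randomization will be stratified by subjects' baseline CNV status (Yes/No) in the fellow (non-study) eye". Focality and pattern are not stratified.

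**Precedence.** Section 8 says a detailed SAP will be final before database lock or unmasking and will override section 8 if they differ, though no discrepancies are expected.

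**The concern.** Baseline lesion area is already used. It is a response, the model has no treatment main effect and so a common intercept, and the random intercept and slope may be correlated. A chance imbalance in area is therefore largely handled, though only through residual error if the variance-components fallback is invoked.

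Focality and junctional-zone pattern are different. They are judged before randomization by a masked reader, they are not balanced by design, and they do not enter the model. If either is related to growth rate, two things follow:
- the slope variation it explains stays in the standard error of both primary contrasts;
- a chance imbalance between groups moves the estimated slope difference and is not corrected.

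Under a linear mixed model, adjustment by covariate-by-time terms targets the same slope difference, so the primary question does not change. What is at stake is precision, not validity.

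**Working it through.** **Inputs (section 8.6).** SD of lesion area 4 mm²; within-subject correlation 0.95; slopes 2, 1.4 and 1.45 mm²/yr, so differences of 0.60 (Q4W) and 0.55 (Q8W); 106 per analysed group; 10% dropout; two-sided 5%. Visits at 0, 24 and 52 weeks (8.3.1.2), so t = 0, 24/52, 1 years.

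**Step 1. Reproduce the stated power, with no covariates.**
- Completers per group: 106 × 0.9 = 95.4.
- Residual variance: 16 × (1 − 0.95) = 0.8.
- Sum of squares of t about its mean: 0.501.
- Observed-slope variance: 0.8 / 0.501 = 1.597 (SD 1.264 mm²/yr).
- SE of a slope difference: √(2 × 1.597 / 95.4) = 0.183.
- Power, Q4W: Φ(0.60/0.183 − 1.96) = 90.6%.
- Power, Q8W: Φ(0.55/0.183 − 1.96) = 85.2%.

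These match the stated figures of about 90% and 85%. A generalized least squares calculation for the stated model under compound symmetry, with the dropout assumed to be half after baseline and half after Week 24, gives 91.6% and 86.4%. The stated power does not depend on covariates.

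**Step 2. What a covariate could remove.** Let s be the share of the 1.597 that is true between-subject slope variance, and r the share of that part explained by the features. The SE is multiplied by √(1 − s·r). The documents give neither s nor r, so both are assumed.

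| Assumption | Explained, r | Q4W power | Q8W power |
|---|---|---|---|
| No covariates | – | 90.6% | 85.2% |
| s = 0 (compound symmetry) | any | no change | no change |
| s = 0.5 | 5% | 91.3% | 86.1% |
| s = 0.5 | 10% | 92.0% | 87.0% |
| s = 0.5 | 15% | 92.6% | 87.8% |
| s = 1 (r is a share of total observed-slope variance) | 5% | 92.0% | 87.0% |
| s = 1 | 10% | 93.3% | 88.7% |
| s = 1 | 15% | 94.5% | 90.3% |

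The s = 0 row matters. Step 1 builds the 1.597 entirely from residual error. Read that way, the planning inputs contain no true slope variance, and a baseline covariate cannot explain independent within-subject error. The fitted model does include a random slope, so the plan allows for some between-subject variation, but it does not say how much.

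**Step 3. Which terms are needed.** In a simulation of 3,000 runs, with the covariate explaining 20% of the variance of the 52-week change (assumed), the SE of the Q4W slope difference was 0.183 with no covariate, 0.182 with a main effect only and 0.164 with the covariate-by-time term. A main effect alone does almost nothing for a slope contrast.

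**Step 4. Chance imbalance, as an illustration.** Suppose one evenly split binary feature explained 10% of the observed-slope variance.
- Difference in slope between its levels: 2 × √(0.10 × 1.597) = 0.80 mm²/yr.
- SD of the between-group difference in its proportion: √(2 × 0.25 / 106) = 0.069, about 7 percentage points.
- Effect of a 10-point imbalance: 0.10 × 0.80 = 0.08 mm²/yr, against planned effects of 0.60 and 0.55.

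**The case against.** Several stronger readings are tempting, and the documents do not support them.

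- **That the reading centre must classify every eye on both features, so the data already exist.** Criterion 3(d) is met by either banded or diffuse; the reader has only to rule out eyes without the pattern. Criterion 3(b) can be applied by checking the largest lesion, since a unifocal eye meeting the 2.5 mm² minimum passes automatically. Nowhere is either grade said to be recorded as a data field. If one is not held, stored images would have to be regraded.
- **That the sponsor regards the pattern as prognostic.** Criterion 3(d) gives no reason. Even if excluding eyes without the pattern implied a view on progression, it would say nothing about banded against diffuse, the only contrast left after exclusion.
- **That precision is being given away for nothing, or that power falls short.** The planned power is met without covariates, type I error and the estimand are unaffected, and randomization with the model-based SE already allows for chance imbalance on average. The possible gain runs from zero upwards. The s = 1 rows require all the observed-slope variance to be true between-subject variance, with no measurement error.

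The SAP announced in section 8 may also add such terms; the text available shows none.

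What survives is narrower. The model has no baseline lesion feature beyond area, the two features lie within a masked pre-randomization assessment, and pre-specified adjustment costs little even if they prove uninformative.

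**Conclusion.** The point holds as a low-cost improvement, not as a flaw in the plan. The gain in stand-alone power is nil if the features explain no true slope variance. It is about 1 to 2 points for Q4W and 1 to 3 for Q8W if half the observed-slope variance is between subjects and the features explain 5% to 15% of that half. It is about 1 to 4 points for Q4W and 2 to 5 for Q8W if they explain 5% to 15% of the whole. All of these rest on an assumed R-squared beyond baseline area. The adjusted analysis would also correct a realised imbalance in either feature, which the planned model cannot. The choice is credible only if made before unmasking.

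**What to change.** Before unmasking:

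1. Confirm with the central reading centre whether its screening record holds a unifocal/multifocal grade and a banded/diffuse grade.
2. For each grade held, add a main effect and a covariate-by-time interaction to the primary model in 8.3.1.2, the synopsis and the SAP. Keep the terms whatever their p-values.
3. Place ungradable or missing grades in a category stated in advance.
4. Report the unadjusted model as a sensitivity analysis.
5. State the expected R-squared and its source, or say that none is assumed. Leave the section 8.6 power statement as it is.

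The cost is wording in the protocol and SAP, the check with the reading centre and, where a grade exists, its transfer to the analysis dataset. With both features as two-level factors this adds up to four fixed effects among 318 subjects; an ungradable category, if used, adds its own terms. If neither grade is held, the primary model can stay as it is.
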